#### **14.3.2 Analysis of the other efficacy variables**

All other efficacy variables will be analyzed for all subjects in the RS.

Binary variables will be summarized using frequency tables by each visit. Generally, the estimand structure for binary other efficacy variables is as described below. Note that further details will be provided in the SAP.

1. Population = Subjects enrolled according to the protocol-specified inclusion/exclusion criteria and randomized to IMP.
2. Subject-level outcome = The given variable and time point being summarized (eg, ACR50 at Week 24)
3. Intercurrent event handling = An intercurrent event is defined as discontinuation of study treatment prior to the time point being summarized. A composite strategy will be implemented in which a positive clinical outcome is defined as achieving the given variable at the specified time point and not discontinuing study treatment through that time point.
4. Population-level summary measure = Unadjusted proportion of responders

Any missing data that is not preceded by an intercurrent event as described above will be imputed based on NRI as described for the primary and secondary efficacy variables.

Continuous variables will be summarized using descriptive statistics by each visit. Generally, the estimand structure for continuous other efficacy variables is as described below. Note that further details will be provided in the SAP.

1. Population = Subjects enrolled according to the protocol-specified inclusion/exclusion criteria and randomized to IMP.
2. Subject-level outcome = The given variable and time point being summarized (eg, change from Baseline in HAQ-DI at Week 36)
3. Intercurrent event handling = An intercurrent event is defined as discontinuation of study treatment prior to the time point being summarized. A hypothetical strategy will be implemented in which outcomes for subjects without an intercurrent event are as observed at the given time point, and outcomes for subjects with an intercurrent event are treated as though they had completed the randomized study treatment through the time point being summarized. A multiple imputation strategy will be used to impute data following an intercurrent event.
4. Population-level summary measure = Unadjusted mean

---

Any missing data that are not preceded by an intercurrent event as described above will be imputed based on a predefined multiple imputation model as described for continuous secondary efficacy variables.

Other binary and continuous efficacy variables will also be summarized based on observed case data (ie, subjects with missing data or who have prematurely discontinued study treatment are treated as missing). Further, binary outcomes will be summarized using the modified composite estimand.

Time to ACR20/50/70 response will be estimated and presented using the Kaplan-Meier product-limit method for each treatment. Time to a given response will be defined as the length in days from Baseline until the first date when the response is achieved. Subjects who discontinue study treatment prior to achieving a response will be censored at the date of study treatment discontinuation. Subjects in the placebo group who are rerandomized at Week 16 without achieving response will be censored at the date of the Week 16 Visit. The median time to response, including the 2-sided 95% CI, will be calculated for each treatment. Between group differences will be analyzed with a log-rank statistic.

The time to ACR20/50/70 endpoints with missing data that are not preceded by an intercurrent event as described above will be imputed based on a predefined multiple imputation model as described for the primary efficacy variable.

The time to ACR20/50/70 endpoints will also be analyzed using observed case (OC) data.

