## **5.3 Treatment Period**

### **5.3.1 Double-Blind Treatment Period**

During the Double-Blind Treatment Period, subjects will be randomized 3:2:1 (stratified by region and bone erosion [0,  $\geq$ 1]) to 1 of 3 blinded treatments.

Investigational medicinal product treatment details are provided in [Section 7.2](#). Visit windows of  $\pm$ 2 days are allowed for all visits through Week 16. The visit window is relative to the Day 1 (Baseline) Visit.

Bimekizumab, adalimumab, and placebo will be administered sc by unblinded study personnel at the clinical site.

The time between IMP doses should be  $\geq$ 12 days and  $\leq$ 16 days during the Double-Blind Treatment Period. The Double-Blind Period is 16 weeks in duration. At Week 16, subjects will transition from the double-blind, placebo-controlled treatment into the 36-week Active Treatment-Blind Period, as discussed in [Section 5.3.2](#).

Subjects withdrawing early from the study will undergo the Early Termination (ET) Visit assessments and will enter the SFU Period. Subjects who withdraw from IMP during the Double-Blind Period will be encouraged to return for all scheduled visits up to Week 52 and for the SFU Visit (20 weeks after their final dose of IMP), as applicable.

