### **5.3.2 Active Treatment-Blind Period**

After the 16-week Double-Blind Treatment Period, subjects will enter the 36-week Active Treatment-Blind Period. At the Week 16 Visit, subjects will be allocated to treatment regimens as follows:

- Subjects in the bimekizumab 160mg sc Q4W group will continue to receive bimekizumab 160mg Q4W
- Subjects in the adalimumab 40mg sc Q2W group will continue to receive adalimumab 40mg sc Q2W
- Subjects in the placebo group will be reallocated to bimekizumab 160mg sc Q4W

Bimekizumab and adalimumab will be administered sc by unblinded study personnel at the clinical site. The first dose in the Active Treatment-Blind Period will be administered at Week 16 after all assessments have been completed. After Week 16, if the subjects are not responding adequately as per Investigators' judgement, rescue therapy will be allowed as described in [Section 5.4](#).

Visit windows of  $\pm$ 3 days are allowed for all visits after Week 16.

The time between doses during the Active Treatment-Blind Period should be  $\geq$ 11 days and  $\leq$ 17 days.

Subjects who withdraw early from the study will undergo the ET Visit assessments and will enter the SFU Period. Subjects who withdraw from IMP during the Active-Treatment-Blind Period will be encouraged to return for all remaining scheduled visits up to Week 52 and the SFU Visit (20 weeks after their final dose of IMP), as applicable.

---

At the completion of the Active Treatment-Blind Period, Investigators should discuss treatment options with the subject. Subjects who complete PA0010 will be given the opportunity to enter an extension study at Week 52.

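### Censoring only placebo nonresponders, each on their own Week 16 visit date, inflates the placebo time-to-ACR curve at the end of the Week 16 window and biases the log-rank test against bimekizumab

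*Protocol*

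**What the plan says.** Four provisions in the protocol combine.

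- **Event time.** Section 14.3.2 defines time to response as "the length in days from Baseline until the first date when the response is achieved". That is an actual date, not a nominal week.
- **Censoring.** The same section says that placebo subjects "rerandomized at Week 16 without achieving response will be censored at the date of the Week 16 Visit". The only other censoring rule there is "Subjects who discontinue study treatment prior to achieving a response will be censored at the date of study treatment discontinuation". No Week 16 censoring is given for the other arms, and Section 5.3.2 states "Subjects in the bimekizumab 160mg sc Q4W group will continue to receive bimekizumab 160mg Q4W".
- **Analysis.** Time to response is "estimated and presented using the Kaplan-Meier product-limit method for each treatment", with medians and 95% confidence intervals. "Between group differences will be analyzed with a log-rank statistic". Section 14.2 sets a two-sided 5% level for all tests unless stated otherwise.
- **Visit timing.** Section 5.3.1 allows ±2 days: "days are allowed for all visits through Week 16". Week 16 is 112 days after Baseline, so the visit may fall on days 110 to 114.

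Nothing in the protocol assigns nominal visit days or a common cut-off to this endpoint.

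**The concern.** ACR response can be established only at a visit. A placebo subject assessed on day 110 and found not to respond cannot become a responder on days 111 to 114, because no further assessment is due in the window. Kaplan-Meier censoring on day 110 nevertheless treats that subject as someone who might still have responded on those days. Later placebo responders are divided by only the placebo subjects not yet seen, so the daily hazards add up to more than the true Week 16 hazard. Censoring is tied to the very assessment that decides the event, so it is informative by construction.

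Bimekizumab nonresponders seen on day 110 stay in the denominator. The two arms are therefore handled differently within the same five days. In the log-rank test, late-window risk sets hold few placebo subjects, all still able to respond, against nearly all bimekizumab nonresponders, most already assessed. Expected placebo events come out too low.

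At stake are the end of the plotted placebo curve, the displayed gap between arms and the log-rank p-values for ACR20, ACR50 and ACR70.

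**Working it through.** **Inputs from the protocol.** 420 bimekizumab and 280 placebo subjects; ACR50 of 43.8% and 16% (Section 14.9.1); two-sided 5% level (Section 14.2); ±2-day window (Section 5.3.1); full ACR assessments at Weeks 2, 4, 8, 12 and 16 (Table 5-1).

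**Assumptions not in the protocol.** Of the 16% placebo first responses, 12 points arise before Week 16 and 4 at Week 16. The spread of visit days inside the window is varied. There is no dropout.

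**Step 1, the plan's own figures.** 43.8 − 16 = 27.8 points. Odds ratio = (0.438/0.562)/(0.16/0.84) = 4.09. Both match Section 14.9.1. With every visit on its target day, the simulated log-rank size under equal arms is 4.8%, so the test holds its level when there is no visit spread.

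**Step 2, placebo Kaplan-Meier in large samples.** Let p = 4/88 = 0.0455 be the chance of first response at Week 16 given none before, v_j the share of Week 16 visits on day j, and r_j the share not yet made at the start of day j. The protocol's rule gives

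KM = 1 − 0.88 × Π(1 − p·v_j/r_j); the correct value is 1 − 0.88 × (1 − p) = 16.0%.

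| Visit days 110 to 114 | v_j/r_j | Product | KM, day 112 | KM, day 114 |
|---|---|---|---|---|
| Uniform | 1/5, 1/4, 1/3, 1/2, 1 | 0.900 | 15.1% | 20.8% |
| 5/15/60/15/5% | 0.05, 0.158, 0.75, 0.75, 1 | 0.882 | 15.8% | 22.4% |
| 0/5/90/5/0% | 0, 0.05, 0.947, 1, – | 0.911 | 16.0% | 19.8% |

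The overshoot arises on the days after the target day. It persists when 90% of visits are on target.

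**Step 3, log-rank with equal arms and uniform visit days.** Each day has 280 × 0.04/5 = 2.24 placebo and 420 × 0.04/5 = 3.36 bimekizumab events, 5.6 in all. Expected placebo events are 5.6 × the placebo share of those at risk.

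| Day | Placebo at risk | Bimekizumab at risk | Expected placebo events |
|---|---|---|---|
| 110 | 246.4 | 369.6 | 2.24 |
| 111 | 197.1 | 366.2 | 1.96 |
| 112 | 147.8 | 362.9 | 1.62 |
| 113 | 98.6 | 359.5 | 1.20 |
| 114 | 49.3 | 356.2 | 0.68 |

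Observed 11.2 less expected 7.7 leaves 3.5 spurious placebo events. The variance, without tie correction, is 84 earlier events × 0.24 plus 5.6 × (0.240 + 0.227 + 0.206 + 0.169 + 0.107) = 20.2 + 5.3 = 25.5. The mean Z is 3.5/√25.5 = 0.69 instead of 0. The size is then about P(N > 1.27) + P(N < −2.65) = 10.2% + 0.4% = 10.6%.

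**Step 4, simulated size under equal arms (2,000 to 15,000 trials per setting, several independent runs).**

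| Visits on target day | Log-rank size |
|---|---|
| 100% | 4.8% |
| 90% | 5.0-5.3% |
| 80% | 5.8-6.7% |
| 60% | 8.1-9.5% |
| Uniform | 10.7-12.2% |

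In the 15,000-trial uniform run the 11.4% splits into 11.0% favouring placebo and 0.45% favouring bimekizumab. The size also depends on how many first responses arise at Week 16. With an assumed 24% by Week 16, 8 points of it at that visit, it is 9.0-20.4% over spreads from 80% on the day to uniform.

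**Step 5, real differences, uniform visit days.** At 43.8% vs 16%, |Z| falls from about 7.7 to about 7.0 and power stays at 100%. The displayed gap shrinks from 27.8 to about 43.8 − 20.8 = 23 points. For an assumed 24% vs 16%, power is 45% under the protocol's rule and 72% on scheduled visit days.

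**Step 6, remedies.** On scheduled days the size is 4.9% (15,000 trials) and placebo reads 16.0%. Censoring placebo nonresponders at day 114 also gives about 5%, within simulation error, with unbiased curves. Censoring both arms on their own Week 16 dates restores the level (4.6-5.1%) but lifts both curves to about 20.8%.

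**The case against.** Much of the case on the other side stands.

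- **Visit spread is unknown.** A reader might infer that the log-rank test misses its 5% level outright. The protocol gives only the window, not how visits fall inside it, and with 90% or more on the target day the size is close to 5%. The level error is conditional.
- **Only the tail of the curve is wrong.** A reader might take the whole Week 16 placebo estimate to be inflated. At day 112 it reads about 15-16%; the excess arises on days 113 and 114.
- **The bias does not help the drug.** False claims in favour of bimekizumab become rarer than the nominal 2.5%.
- **The endpoint is exploratory.** Time to ACR response is listed in Section 4.3.1 and lies outside the fixed sequence in Section 14.3.1. The Week 16 ACR responder analyses are proportions by visit and are untouched.
- **A false placebo median** would need placebo response near 43.8%, where the curve would read 52-54%. The protocol assumes 16%.
- **The active arms' last visit.** A reader might expect the same artefact there. Section 14.3.2 states no censoring rule for that visit, so the protocol does not support the claim.
- **The SAP may add detail.** Section 14 says so. Added detail does not reverse a stated rule, however, and an SAP that followed Section 14.3.2 literally would inherit the error.

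**Conclusion.** The concern holds in a limited form. The rule is stated, it treats the two arms differently within the Week 16 window, and it gives a wrong placebo curve when the window closes: about 20-23% for an assumed true 16%, in every visit spread tried. Bimekizumab is unaffected. The log-rank size under equal arms runs from near 5% (tight visit timing) to about 11-12% (uniform), with the excess almost wholly in favour of placebo. These figures rest on an assumed 4 points of first response at Week 16, assumed visit spreads and no dropout. The curve error disappears only if all Week 16 visits fall on the same study day.

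The documents do not support reading this as a threat to the primary conclusion, to the family-wise error or to the detection of an effect as large as the one assumed. It is a correctable error in an exploratory analysis.

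**What to change.** In Section 14.3.2, define response and censoring times by scheduled visit day, and state that events precede censoring at the same visit. This alone restores both the curve and the level; bimekizumab need not also be censored at Week 16.

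If actual dates are to be kept, censor placebo nonresponders at the close of the Week 16 window (day 16 × 7 + 2 = 114) rather than on their own visit date. Neither arm should be censored on its own actual Week 16 date: doing so in both arms repairs the test but inflates both curves.

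The cost is one sentence and one derived time variable, with no new data or subjects. Under the first option time to response is reported on the visit grid, which is the resolution the assessments have in any case.

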#### 14.3.1.1 Analysis of the primary efficacy variable

The primary efficacy variable will be analyzed for all subjects in the RS.

---

The primary endpoint is the ACR50 response at Week 16. The primary efficacy analysis will evaluate the composite estimand in the RS. The composite estimand combines the clinically meaningful improvement from Baseline in ACR50 response and not discontinuing treatment early. This composite estimand is similar to nonresponder imputation (NRI).

The following 4 attributes describe the estimand that will be used to define the treatment effect of interest for the primary efficacy analysis:

1. Population = Subjects enrolled according to the protocol-specified inclusion/exclusion criteria and randomized to IMP.
2. Subject-level outcome = ACR50 at Week 16.
3. Intercurrent event handling = An intercurrent event is defined as discontinuation of study treatment prior to Week 16. A composite strategy will be implemented in which a positive clinical outcome is defined as achieving ACR50 at Week 16 and not discontinuing study treatment through Week 16.
4. Population-level summary measure = Conditional odds ratio comparing bimekizumab to placebo.

As the ACR response is based on 7 different component scores, it is necessary to consider various data scenarios that could impact the calculation of response. The rules described here are applicable in the context of the calculation of ACR response and may differ from the rules applied for calculating and summarizing the components individually (some values may need to be imputed for component analysis but are not required here to evaluate ACR response).

The following rules will be applied prior to invoking any imputation analysis at the variable level:

- If a subject has a component value that is equal to 0 at Baseline and the post-Baseline value is greater than or equal to 0, then the percent improvement for that component will be treated as 0 for purposes of ACR response calculations.
- If a subject has component values that are missing at Baseline, then the percent improvement for that component will be treated as missing for purposes of ACR response calculations.

Observed data will be used to calculate ACR response where possible. In case of partial missing data where an observed response may be calculated, imputed data will not change the result.

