Missing data at Week 16 that are not preceded by an intercurrent event, and any data after an intercurrent event will be imputed as non-responders.

The statistical hypothesis for the ACR50 response at Week 16 is that the conditional odds ratio for ACR50 response in the bimekizumab treatment compared with placebo treatment is equal to 1.

A logistic regression model will be used to assess the treatment effect on ACR50 response at Week 16. The model will include a fixed effect for treatment. The suitability of including the randomization stratification variables, region and bone erosion at Baseline will be assessed and will be added to the model if appropriate. Comparisons will be made using the 2-sided Wald test at a significance level of  $\alpha=0.05$  (ie,  $H_1$  in [Figure 14-1](#)). The odds ratio versus placebo, p-value, and the 95% CI will be calculated.

---

Any use of prohibited or rescue medications through Week 16 would constitute an important protocol deviation which would be accounted for when the sensitivity analysis based on the PPS is performed (see [Section 14.3.1.1.1](#)).

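### Missing time-to-ACR data are sent to a multiple imputation model that the primary analysis no longer uses, and treatment discontinuers are censored where the main ACR analyses count them as non-responders

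*Protocol*

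**What the plan says.** The last paragraphs of Protocol Section 14.3.2 set out time to ACR20, ACR50 and ACR70 response. Time to response "will be estimated and presented using the Kaplan-Meier product-limit method for each treatment", and "Between group differences will be analyzed with a log-rank statistic". On stopping treatment: "Subjects who discontinue study treatment prior to achieving a response will be censored at the date of study treatment discontinuation". Data that are missing without a preceding intercurrent event "will be imputed based on a predefined multiple imputation model as described for the primary efficacy variable". An observed-case version is also planned.

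Section 14.3.1.1, to which that sentence points, says: "Missing data at Week 16 that are not preceded by an intercurrent event, and any data after an intercurrent event will be imputed as non-responders". Its estimand is composite: "A composite strategy will be implemented in which a positive clinical outcome is defined as achieving ACR50 at Week 16 and not discontinuing study treatment".

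For the other binary variables, Section 14.3.2 says that missing data without a preceding intercurrent event "will be imputed based on NRI as described for the primary and secondary efficacy variables". It introduces the composite structure for them with the words "Generally, the estimand structure for binary other efficacy variables is as described below".

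**The concern.** There are two separate problems.

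The first is a cross-reference to a rule that is not there. An analyst who follows it to the primary analysis finds non-responder imputation. The choice changes the data: multiple imputation can turn a missed visit into a first response and so bring the event date forward, whereas under non-responder imputation a first response can occur only at a visit where ACR status was determined.

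The second is censoring at discontinuation. Kaplan-Meier treats a censored subject as still able to respond at the rate of those who stay. Section 5.4 allows withdrawal from study treatment at any time for subjects judged not to be responding, so the reason for censoring is probably related to the outcome. The curves, medians and log-rank tests would then describe a different quantity from the main ACR response rates reported beside them, and the Protocol does not say so.

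**Working it through.** **1. The imputation rule, text against text**

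- Time to ACR response (14.3.2): multiple imputation, by reference to the primary variable.
- Primary analysis (14.3.1.1): missing data, and all data after an intercurrent event, are non-response.
- Other binary variables (14.3.2): non-responder imputation, by reference to the primary and secondary variables.
- Sensitivity analyses of the primary variable (14.7): item 1 uses multiple imputation, with the intercurrent event narrowed to discontinuation for an adverse event or lack of efficacy. Item 3 uses it within a treatment policy strategy.

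Two sentences in Section 14.3.2 thus cite the primary analysis and attribute opposite methods to it. Section 14.7 does not settle the matter. The time-to-response sentence relies on the intercurrent event as already described in 14.3.2, which is any discontinuation of study treatment. Neither multiple imputation analysis in 14.7 handles intercurrent events in that way.

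**2. Direction of the censoring effect within an arm**

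Censoring removes a non-responding discontinuer from the risk set. Keeping that subject leaves the later events unchanged and enlarges the denominators, so each later step of the curve is smaller. The censored curve is therefore never below the other, whatever the discontinuation rate.

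**3. Size, as an illustration**

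The Protocol gives no figure for time to response and no discontinuation rate.

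Inputs from Section 14.9.1: ACR50 of 43.8% for bimekizumab and 16% for placebo. Check: 43.8 − 16 = 27.8 points, and (0.438/0.562)/(0.16/0.84) = 4.09, both as stated there. These are response rates at a visit and serve here only as a scale.

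Assumptions: discontinuation by Week 16 of 2% to 20%, and constant, independent hazards of response and discontinuation.

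Formulas, with T = 16 weeks, p the Kaplan-Meier value and d the discontinuation proportion:

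- λ = −ln(1 − p)/T and μ = −ln(1 − d)/T
- proportion responding before stopping = λ/(λ + μ) × [1 − exp(−(λ + μ)T)]

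Bimekizumab at d = 5%: λT = 0.576, μT = 0.051, so 0.918 × (1 − 0.562 × 0.95) = 0.918 × 0.466 = 42.8%.

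| Assumed discontinuation | Bimekizumab (censored 43.8%) | Gap, points | Placebo (censored 16.0%) | Gap, points |
|---|---|---|---|---|
| 2% | 43.4% | 0.4 | 15.8% | 0.2 |
| 5% | 42.8% | 1.0 | 15.6% | 0.4 |
| 10% | 41.8% | 2.0 | 15.2% | 0.8 |
| 15% | 40.7% | 3.1 | 14.8% | 1.2 |
| 20% | 39.7% | 4.1 | 14.4% | 1.6 |

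**4. Between arms**

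The censored difference is 27.8 points. With discontinuers counted as non-responders it becomes:

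- 27.2 at 5% discontinuation in both arms
- 26.6 at 10% in both arms
- 24.1 at 20% on bimekizumab and 5% on placebo
- 28.4 at 5% on bimekizumab and 20% on placebo

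**The case against.** The strongest reply is that the Protocol breaks no rule of its own by censoring. The composite structure in 14.3.2 is offered as a general pattern for binary variables at a time point, summarized by a proportion. Time to response is a different kind of variable with its own explicit rule, and an on-treatment or hypothetical target is legitimate; the Protocol uses a hypothetical strategy for its continuous variables. That stands: censoring here is a different, undeclared estimand, not a breach of a stated rule.

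A reader might infer that multiple imputation has been abandoned for the primary variable. It has not. Section 14.7 keeps it for sensitivity analyses; it is only no longer the main method.

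A reader might also infer that every other binary ACR analysis counts discontinuers as non-responders. That is not so either. The modified composite, treatment policy and observed-case analyses in 14.3.1.1.1 and 14.7 each handle some or all discontinuers differently. The contrast is with the main analyses only.

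Two limits on the size also stand. Under the independence assumed above, the gap is the distance between two estimands, not bias in the Kaplan-Meier estimate. Also, a curve of first response can exceed visit-wise response rates even with no discontinuation, because a subject who later loses response stays counted. Changing the censoring rule would not remove that difference.

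What the reply does not answer is the imputation sentence. It fixes a rule that conflicts with the section it cites, so leaving detail to the SAP does not cure it.

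**Conclusion.** The imputation reference is wrong in the current text and needs correcting; this part rests on wording alone. The censoring point holds in a smaller form. Censoring is likely to be informative, and each arm's curve lies at or above the curve with discontinuers as non-responders. At Week 16 the gap is about 1 point for bimekizumab and 0.4 for placebo at 5% discontinuation, rising to about 4 and 1.6 points at 20%. These sizes rest on assumed discontinuation rates and constant, independent hazards. Any further error because those who stop are poorer responders is not included.

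It would be tempting to conclude that the analysis overstates the treatment effect. The Protocol does not support that: the between-arm difference may be overstated or understated, depending on which arm discontinues more. Section 4.3.1 lists time to response among the other efficacy variables, outside the fixed testing sequence, so the primary conclusion is not affected.

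**What to change.** - **Imputation.** Replace the sentence in Section 14.3.2 with: a visit with missing ACR status is treated as no response at that visit. If a multiple imputation version is wanted, keep it as a named sensitivity analysis.
- **Discontinuers.** In the main time-to-response analysis, keep subjects who stop treatment before responding in the risk set as non-responders to the end of the period, which is Week 16 for the placebo comparison. Alternatively, report cumulative incidence with discontinuation as a competing event. Retain the censored Kaplan-Meier version as supportive, and state which estimand each version addresses.

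The cost is a few lines in Section 14.3.2 and one programming rule. The curves will be slightly lower. Sample size, the testing hierarchy and study conduct are unchanged.
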